## **6.1 Correlative Science**

PD-L1 expression may be assessed by immunohistochemistry as previously described.

Optional Tumor: If optional tumor tissue is collected at the time of ablation, and stored as per routine pathology procedures at Rhode Island Hospital/Lifespan, this may be retrospectively analyzed for PDL1 expression.

Optional whole blood: Patients will have the option of providing an additional 10 cc of whole blood (3 6ml purple top tubes) to be sent to the laboratory of [name] at Rhode Island hospital to assess the effect of nivolumab and ablation on lymphocyte populations. The blood will be drawn at study entry with pre-drug cycle lab work, then before and after each ablation at the times specified below.

### Correlative studies for immune function

The impact of the encounter with damaged and dying cells on the immune system can range from induction of tolerance to enhanced immune responses. One of the consequences of ablation could be enhanced tumor immunity. To test this possibility, the following correlative studies will be done at the following time-points: baseline before nivolumab, after nivolumab/ before first ablation, after ablation and prior to cycle 2 nivolumab, approximately 3 months post ablation and then approximately 6 months post ablation (approximately 3 months later). If patient has a second ablation, a set will be taken before and after ablation. At each time point 3, 6mL purple top tubes will be collected and sent to the laboratory. Initially the samples will be processed and the plasma, microvesicles and cells collected and stored at -80°C for further studies. These samples will be used to study the presence of antigen circulating in the blood, the impact of nivolumab and ablation on distribution of subpopulations based on immunophenotyping and functional studies to determine if anti-cancer immune responses have been induced by these therapeutic interventions and if detected changes correlate with response.

The blood samples when collected should be stored at room temperature, the laboratory notified (cc BrUOG on email to [name] laboratory) and the samples transported to the laboratory for processing the same day. Research staff will not be processing samples, staff in [name] laboratory will be processing. Samples are to be labeled with study number (BrUOG 317), patient initials, patient study number and time point.

1. Spin at 1000 rpm and collect platelet rich plasma
2. The plasma will be process further by spinning at 3000 rpm
3. The supernatant will then be centrifuged at 100000 x g for 1 hour.
4. The pellet will be resuspended in PBS containing 1% DMSO and stored at -80° C.
5. The plasma will be collected after the ultracentrifuge step and will be stored at -80° C.

6. The pellet will be resuspended in PBS containing 1% DMSO and stored at -80°C.
7. Resuspend initial cell pellet in PBS and isolate peripheral blood mononuclear cells (PBMNC) using Ficoll-Hypaque gradient density centrifugation
8. The PBMNC will be frozen down for future studies

## **7.0 RESPONSE ASSESSMENT:**

**7.1. Objective Response Rate by RECIST:** Response Evaluation Criteria in Solid Tumors (RECIST), version 1.1 will be used to assess responses by CT/ MRI but response criteria are modified by the immune-related response criteria as described in section 7.3. The first scheduled assessment of tumor response will be performed approximately 12 weeks after the first dose of nivolumab and approximately every 12 weeks thereafter. Patients in whom a scheduled scan showed initial disease progression will be allowed to continue receiving treatment until a confirmatory scan was obtained at least 1 month later. (see section 7.3)

Use of RECIST to clinically assess response for patients who progress with sum of target lesion is > 20 % then should use IrRC (if patient is asymptomatic, no vital organ involved etc.)

**7.2.** Overall responses derived from investigator reported data, with assessment according to immune-related response criteria.

## **7.3 Treatment Beyond Disease Progression**

Accumulating evidence indicated a minority of subjects treated with immunotherapy may derive clinical benefit despite initial evidence of progressive disease (PD).

Subjects treated with nivolumab will be permitted to continue treatment beyond initial RECIST 1.1-defined PD as long as they meet the following criteria: (REQUIRED for site to document and confirm all are true and submit to BrUOG)

- Investigator-assessed clinical benefit and do not have rapid disease progression
- Tolerance of study drug
- Stable performance status
- Treatment beyond progression will not delay an imminent intervention to prevent serious complications of disease progression (eg, CNS metastases)
- A radiographic assessment/scan should be performed within 6 weeks **and at least a month after original PD to determine whether there has been a decrease in the tumor size or continued PD.** The assessment of clinical benefit should be balanced by clinical judgment as to whether the subject is clinical deteriorating and unlikely to receive any benefit from continued treatment with nivolumab
- If the investigator feels that the nivolumab subject continues to achieve clinical benefit by continued treatment, the subject should remain on the trial and continue to receive monitoring according to the Time and Events Schedule.

**For the subjects who continue nivolumab study therapy beyond progression, further progression is defined as an additional 10% increase in tumor burden volume from time of initial PD.** This includes an increase in the sum of all target lesions and/or the development of new measurable lesions. Treatment should be discontinued permanently upon documentation of further disease progression.

New lesions are considered measurable at the time of initial progression if the longest diameter is at least 10 mm (except for pathological lymph nodes which must have a short

axis of at least 15 mm). Any new lesion considered non-measurable at the time of initial progression may become measurable and therefore included in the tumor burden volume if the longest diameter increases to at least 10 mm (except for pathological lymph nodes which must have a short axis of at least 15 mm).

Global deterioration of health status requiring discontinuation of treatment without objective evidence of disease progression at the time should be reported as symptomatic deterioration. Every effort should be made to document objective progression (ie, radiographic confirmation) even after discontinuation of treatment.

The assessment of clinical benefit should take into account whether the subject is clinically deteriorating and unlikely to receive further benefit from continued treatment. All decisions to continue treatment beyond initial progression must be discussed in the study records.

#### **7.4 Modified immune-related response criteria (irRC), derived from RECIST 1.1**

This new classification is based on the recent learning from clinical studies with cancer immunotherapies that even if some new lesions appear at the beginning of a treatment or if the total tumor burden does not increase substantially, tumor regressions or stabilizations might still occur later. The irRC were created using bidimensional measurements (as previously widely used in the World Health Organization criteria). For this trial, the concepts of the irRC are combined with RECIST 1.1 to come up with the modified irRC.

For modified irRC, only target and measurable lesions are taken into account. In contrast to the RECIST 1.1 criteria, the modified irRC criteria (a) require confirmation of both progression and response by imaging at 12 weeks after initial imaging and (b) do not necessarily score the appearance of new lesions as progressive disease if the sum of lesion diameters of target lesions (minimum of 10 mm per lesion, maximum of 5 target lesions, maximum of 2 per organ) and measurable new lesions does not increase by  $\geq 20\%$ .

The same method of assessment and the same technique should be used to characterize each identified and reported target lesion(s) at baseline, during the trial, and at the end of trial visit. All measurements should be recorded in metric notation. The modified irRC based on RECIST 1.1 are displayed below.

#### **Modified immune-related response criteria are defined as follows:**

New measurable lesions: Incorporated into tumor burden.

New non-measurable lesions: Do not define progression but precludes (irCR).

Overall irCR: Complete disappearance of all lesions (whether measurable or not) and no new lesions. All measurable lymph nodes also must have a reduction in short axis to 10 mm.

Overall irPR: Sum of the longest diameters of target and new measurable lesions decreases  $\geq 30\%$ .

Overall irSD: Sum of the longest diameters of target and new measurable lesions neither irCR, irPR, (compared to baseline) or irPD (compared to nadir).

Overall irPD: Sum of the longest diameters of target and new measurable lesion increases  $\geq 20\%$  (compared to nadir). It is recommended that overall irPD be confirmed by a follow-up CT at least 4-12 from the date first documented.

Overall responses derived from changes in index, non-index, and new lesions are summarized in the table below.

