### **3.0 ELIGIBILITY:**

#### **3.1 Inclusion Criteria:**

3.1.1 Pathologically or cytologically confirmed NSCLC

3.1.2 Stage IIIB or stage IV.

3.1.3 Patient to meet either criterion A or B:

A) Patient must have progressed after at least 1 line of systemic treatment (IV or oral) for metastatic or locally advanced disease. Must provide documentation systemic treatment was for either locally advanced or metastatic. Must also provide scan or assessment to show most recent progression, pre-enrollment certifying progression of disease to meet inclusion eligibility of progression. Radiation does not count as 1 line.

FDA exemption 6/30/15, 6/30/15, 8/17/15 (for LOCR initial), Amendment #1 10/5/15 v 2 HS approval, Amendment # 2 11/9/15, Amendment #3 3/4/16, Amendment # 4 4/7/16, Amendment # 5 6/1/16 V2, Amendment # 6 7/7/16, Amendment # 7 11/16/16, Amendment # 8 2/22/17, Amendment #9 5/22/17

B) Patients progressing within 6 months of completion of neoadjuvant or adjuvant chemotherapy are also eligible without having treatment for metastatic disease (for example patient with stage I disease undergoes resection, receives systemic chemotherapy and then progresses to the liver (now stage IV) within 6 months of chemotherapy). Radiation does not count as 1 line.

3.1.4 Ablation for advanced lung cancer is being considered by the treating physician for treatment or prevention of symptoms such as pain, bleeding or obstruction- Documentation is required in writing by MD for this criterion.

3.1.5 At least 1 site of measurable disease that will not be treated with ablation. Sites to send confirmation on which lesion of measurable disease will not be ablated for tracking of response.

3.1.6 At least 3 weeks since prior systemic treatment and/or radiation therapy for patient's NSCLC (from treatment day 1 on study)

3.1.7. No brain metastases except for patients whose metastases have been removed by surgical resection or have had stereotactic radiation or gamma knife with no evidence of active disease on MRI within 28 days of starting treatment.

3.1.8. Eastern Cooperative Oncology Group (ECOG) Performance Status of 0-2.

3.1.9. Life expectancy of at least 12 weeks.

3.1.10. Required entry laboratory parameters within 14 days of study entry: Granulocytes  $\geq$  1000/ $\mu$ l; platelet count  $\geq$ 75,000/ $\mu$ l; Creatinine  $\leq$  1.5x upper limit normal mg/dl; Bilirubin  $<$  1.5x upper limit normal; AST  $\leq$  3 x upper limit of normal.

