## **4.0 TREATMENT:**

**4.1 Nivolumab:** 3mg/kg up to a maximum dose of 240mg IV over approximately 60 minutes on Day 1 +/- 3 days every 2 weeks until progression for a maximum of 2 years.

It will also not be considered a deviation if a cycle or pre-cycle assessment must be adjusted to accommodate scheduling or holidays. Adjustment must be documented with reason to BrUOG. While efforts should be made to have cycles be every 2 weeks (+/- 3 days), further allowances are allowed as long as cycles are not < 10 days.

**4.2 Ablation:** Either cryoablation or thermal ablation may be performed as per standard institutional policies. Ablation should be performed within 1 week (7 days) of the initial treatment with nivolumab, to occur within the first cycle (14 days) of treatment. Additional ablation procedures may be performed as clinically indicated such as for pain control including the treatment or prevention of pain or obstruction or as per institutional standard of care. There must be a minimum of 60 days between each ablation (60-90 days is preferable). Standard institutional procedures may be used in ablation. One or more than one lesion may undergo ablation as per investigator judgement and institutional standard of care. At least one measurable site of disease cannot be ablated so that it may be followed for response. This location should be chosen at baseline with enrollment-see section 3.1.5

During the same procedural period as ablation, if patient has consented and agreed, a tumor tissue biopsy may be obtained prior to each ablation, as per institutional standard of care. This biopsy may be assessed for future correlative studies such as assessment of PD-L1 by immunohistochemical staining and will allow for correlation to response.

The following treatments must not be administered during the study: Immunotherapy other than the study drug, immunosuppressive drugs [i.e., chemotherapy or systemic corticosteroids except for short term treatment of allergic reactions or for the treatment of immune related adverse events (irAEs)}, or other experimental pharmaceutical products. Short term administration of systemic steroid (i.e., for allergic reactions or the management of irAEs is allowed).

Growth factors (granulocyte colony stimulating factor or granulocyte macrophage colony stimulating factor). Exception: Erythropoietin and darbepoietin alpha may be prescribed at the investigator's discretion.

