#### 6.0 SCHEDULE OF EVALUATIONS / STUDY CALENDAR

Parameter	Pre-study (to be sent to BrUOG prior to registration)	Within 3 days prior to Day 1 of Each Cycle of Nivolumab (approximately every 2 weeks) F	While on Nivolumab therapy (Every 12 weeks approximately every 6 cycles)	Ablation L Cycles 1(1 week after starting drug) and prior to each additional ablation (if performed)	End of Treatment (2 week window provided)	30 days post last dose of drug	FU D
Informed Consent (within 30 days of day 1) *pts are to be re-consented if ICF will be outside 30 day window	X						
Demographics	X						
Conmed log P	X	X	X	X	X		
Nivolumab K		X					
Optional labs: 3, 6ml purple top tubes to [name] at RIH at multiple time points	X	X O		X O			X O
Optional Tissue biopsy				X M			
History G	X			X			
Physical examination	X	X Q			X	X I	
Weight	X	X					
Vital signs	X	X					
Toxicity Assessment	X	X			X	X H	
Performance Status	X	X			X		
CBC, diff, platelet count	X (within 14 days)	X			X		
Na, K, BUN, Cr, AST, ALT, Bili	X (within 14 days)	X			X		
Ca, Mg, PO4	X (within 14 days)	X			X		
INR, TSH	X (within 14 days)						
Pre-Ablation labs: PLT, PT, PTT, INR				(within 2 weeks of ablation up to day of (prior to) N			

Serum Pregnancy E	X (within 7 days of drug)						
CT scan of Chest/abd/pelvis	X AC (with in 6 weeks)		X CJ		X CJ (CT does not need to be repeated if done in prior 2 months)		X D
CT scan or MRI of brain	X(within 6 weeks)		X (only if clinically indicated)		X (only if clinically indicated)		X
EKG B	X						
Survival and Disease status						X	X D

A- CT Scan for disease assessment to be performed within 6 weeks of study entry. Report required. (chest X-ray okay with baseline).

B- EKG within 8 weeks of study entry. Report required

C- An MRI or PET scan may substitute for disease assessment.

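### The irPR sum in Protocol 7.4 does not exclude ablated lesions, so a target that is ablated can create or hide a response in the primary count

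*Protocol*

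**What the plan says.** **Reserved lesion.** Protocol 3.1.5 requires one measurable site that will not be ablated, and adds: "Sites to send confirmation on which lesion of measurable disease will not be ablated for tracking of response". Protocol 4.2 says: "At least one measurable site of disease cannot be ablated so that it may be followed for response". The Appendix B checklist repeats the requirement at registration.

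**Other lesions.** Protocol 4.2 also says: "One or more than one lesion may undergo ablation as per investigator judgement and institutional standard of care". Repeat ablations are allowed, with a limit on spacing: "There must be a minimum of 60 days between each ablation".

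**Timing.** Baseline imaging is before treatment: "CT Scan for disease assessment to be performed within 6 weeks of study entry" (6.0, footnote A). Then "Ablation should be performed within 1 week (7 days) of the initial treatment with nivolumab" (4.2). Then "The first scheduled assessment of tumor response will be performed approximately 12 weeks after the first dose of nivolumab" (7.1).

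**Scoring.** Section 7.2 takes overall response from investigator data under the immune-related criteria. Section 7.4 allows up to five targets, two per organ, and defines partial response as "Overall irPR: Sum of the longest diameters of target and new measurable lesions decreases" by 30% or more. The closing note of 7.4 is the only scoring rule on ablated lesions. It says that enlargement after ablation without suspicious enhancement is not progression, and it says nothing on response.

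**Test.** Protocol 17.1 and the SAP count responses against about 20% for nivolumab alone. Neither says which lesions contribute.

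**The concern.** The eligibility and treatment sections guarantee that an un-ablated lesion exists. They do not say that response is scored on un-ablated lesions only. A site can name one reserved lesion, satisfy 3.1.5, and still list an ablated lesion as a second target. The sum for that patient then mixes the local result of a procedure with the response of the rest of the disease, and the same scans can score as response or non-response according to which lesions were listed.

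This bears on the primary endpoint because the 20% reference is for nivolumab alone, where no lesion was ablated as part of the treatment under study. With decision limits of 5 of 18 and 11 of 33, a small number of misclassified patients can matter.

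**Working it through.** **1. The plan's own figures.** Inputs from Protocol 17.1 and the SAP: p0 = 0.20, p1 = 0.40, 18 then 33 patients, stop at 4 or fewer of 18, reject at 11 or more of 33. The chance of rejecting is the sum over x = 5 to 18 of P(X1 = x) × P(X2 ≥ 11 − x), with X1 binomial(18, p) and X2 binomial(15, p). This gives 0.0458 at p = 0.20 and 0.801 at p = 0.40. The stated 0.05 (as an upper limit) and 80% are reproduced.

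**2. Does ablation fall between the two scans that are compared?** Yes. Baseline CT is before treatment. The first ablation falls at about day 1 to 8, and the first response scan at week 12, about day 84. Adding the 60-day minimum, a second ablation is possible from about day 61 to 68, also before that scan.

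**3. Lesion arithmetic, k equal targets, one ablated.**

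- *Creating a response.* If the ablated target goes to nil and the others do not change, the sum changes by −1/k. Shrinkage of that target alone reaches −30% when it is at least 0.3k.
- *Hiding a response.* If the ablated target keeps its size, the others must shrink on average by 0.3k/(k − 1).

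| k | Sum if ablated target goes to nil | Meets irPR size threshold | Shrinkage needed in the others if it keeps its size |
|---|---|---|---|
| 2 | −50% | yes | 60% |
| 3 | −33% | yes | 45% |
| 4 | −25% | no | 40% |
| 5 | −20% | no | 37.5% |

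The closing note of 7.4 prevents a call of progression when the ablated zone is larger, but it does not restore a response. Suppose an ablated target goes from 40 to 55 mm and an un-ablated one from 40 to 20 mm. The sum goes from 80 to 75 mm, −6%, which is stable disease although the un-ablated lesion halved.

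**4. New lesions.** Decreases are taken relative to baseline (note 1 to the 7.4 table), and a new lesion is not in the baseline sum. Ablating it can only remove an addition. It cannot by itself produce a 30% fall.

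**5. Effect on the test, under assumed shares.** Let m be the share of non-responders in un-ablated disease who are counted as responders only through an ablated target, and d the share of responders who are hidden. The documents give neither.

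| Assumption | Apparent rate | Expected patients of 33 | Chance of rejecting |
|---|---|---|---|
| True 20%, m = 1% | 0.20 + 0.80m = 0.208 | 0.3 | 0.059 |
| True 20%, m = 2% | 0.216 | 0.5 | 0.074 |
| True 20%, m = 5% | 0.240 | 1.3 | 0.134 |
| True 40%, d = 5% | 0.40(1 − d) = 0.380 | 0.7 | 0.733 |
| True 40%, d = 10% | 0.360 | 1.3 | 0.653 |
| True 40%, d = 15% | 0.340 | 2.0 | 0.563 |

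The errors can offset. At a true 20% with m = 2% and d = 8%, the apparent rate is 0.20 × 0.92 + 0.80 × 0.02 = 0.200, and the chance of rejecting is again 0.0458.

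**The case against.** **The intent is clear.** Sections 3.1.5 and 4.2 and the checklist have the un-ablated lesion chosen at baseline and followed for response. The case report forms are attached separately and were not seen; they may apply the intent. This stands as a limit on how often the problem would occur. It does not supply the missing rule, because the text protects one lesion and the sum takes up to five.

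**The endpoint is response to the combination.** Sections 1.1, 17.0 and 17.1 say so, and ablation is part of that treatment; systemic activity appears only in the rationale in section 2.0. This stands. It is why the as-measured result should also be reported, and why a true rate in un-ablated disease is a reading of the aim, not a quantity that the plan defines.

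**Confirmation protects.** Section 7.4 asks for a second scan, but a local effect that lasts will still be there.

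**Stronger readings that do not hold.** A reader might infer that the type I error is inflated. The documents do not support that: frequency and net direction are unknown, and the errors can cancel. A reader might also note that the trial sits exactly on a limit with appreciable probability (4 of 18 with probability 0.215 and 10 of 33 with 0.043 at a true 20%; 5 of 18 with 0.115 and 11 of 33 with 0.093 at 40%) and take these as chances of a reversed decision. They are not. A reversal also needs a misclassified patient in that trial, and that probability is not known.

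**Conclusion.** The concern holds as a gap between the sections that reserve an un-ablated lesion and the rule that scores response. Applied as written, the irPR rule can score a response with no change in un-ablated disease, or hide one. Only patients with an ablated target are open to this in full; an ablated new lesion can at most remove an addition to the sum. The gap in wording is certain. The size of its effect on the primary count is not: the range from 0.059 to 0.134 for false rejection, and from 0.733 to 0.563 for power, rests on assumed shares of 1% to 5% and 5% to 15%, each taken with the other error at zero. The design itself is correct. This should be fixed, because the remedy is cheap and the rule is best settled before responses are counted.

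**What to change.** State the following in Protocol 7.1/7.4 and 17.1 and in the SAP, for response scoring only:

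1. For the primary response endpoint, target lesions are chosen at baseline from measurable lesions not planned for ablation, including the one named under 3.1.5. The target list is recorded at registration.
2. Size change in an ablated lesion, in either direction, does not count toward irPR or irCR and is reported separately as local control.
3. One rule for a target that is ablated later is set in advance. There are two candidates:
   - *Carry its last pre-ablation diameter.* This keeps growth before ablation in the sum. It blocks irCR, and it blocks irPR when the carried diameters exceed 70% of the baseline sum. Carried at baseline size, three of four equal targets allow at most −25%, four of five at most −20%, and 60 mm of 80 mm at most −25%.
   - *Drop it from both the baseline and the follow-up sums.* This avoids those blocks but can remove a growing lesion.

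   Use one as primary and the other as a sensitivity analysis.
4. Response with all lesions as measured is a further sensitivity analysis, since the stated endpoint is response to the combination.

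Progression rules, treatment, N=33 and the 5/18 and 11/33 rules stay as written.

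**Cost.** One added registration item: the visible checklist collects the un-ablated lesion and the type, date and hospital of ablation, but not the full target list. No added patients, visits or scans. Some patients will have fewer targets, and the observed response rate may be slightly lower.

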**Overall Responses Derived from Changes in Index, Non-Index, and New Lesions**

Measurable Response	Non-Measurable Response		Overall Response Using Modified irRC
Index and New, Measurable Lesions	Non-Index Lesions	New, Non-Measurable Lesions	
Decrease 100%	Absent	Absent	irCR 
Decrease 100%	Stable	Any	irPR 
Decrease 100%	Unequivocal progression	Any	irPR 
Decrease $\geq 30\%$	Absent / Stable	Any	irPR 
Decrease $\geq 30\%$	Unequivocal progression	Any	irPR 
Decrease $< 30\%$ to increase $< 20\%$	Absent / Stable	Any	irSD
Decrease $< 30\%$ to increase $< 20\%$	Unequivocal progression	Any	irSD
Increase $\geq 20\%$	Any	Any	irPD

 Decreases assessed relative to baseline

 Assuming that the response (irCR and irPR) and progression (irPD) are confirmed by a second, consecutive assessment at least 4 weeks apart (normally it should be done 6 weeks apart).

Post Ablation changes observed on radiographic studies that are larger in size than preablation masses will not be considered tumor progression if no enhancement within the lesion that suggests tumor growth.

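### irPD in Protocol 7.4 has no minimum rise in millimetres, so at a 10 mm sum a 2 mm rise meets the threshold, and the confirmatory scan that should guard against this is worded three ways

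*Protocol*

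**What the plan says.** Protocol 7.4 gives progression as "Overall irPD: Sum of the longest diameters of target and new measurable lesion increases" by at least 20% compared with nadir. The introduction to 7.4 and its overall-response table use the same percentage. None of the three adds an absolute increase.

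The millimetre figures in section 7 are size thresholds for lesions and nodes, not thresholds for change. Targets are limited to "minimum of 10 mm per lesion, maximum of 5 target lesions, maximum of 2 per organ". In 7.3, "New lesions are considered measurable at the time of initial progression if the longest diameter is at least 10 mm", with 15 mm short axis for nodes. Inclusion criterion 3.1.5 asks for "At least 1 site of measurable disease that will not be treated with ablation".

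Confirmation of progression appears in 7.4 in three forms:
- The introduction says the criteria "require confirmation of both progression and response by imaging at 12 weeks after initial imaging".
- The definition list says "It is recommended that overall irPD be confirmed by a follow-up CT at least 4-12 from the date first documented", with no time unit.
- Footnote 2 of the table assumes that response and progression "are confirmed by a second, consecutive assessment at least 4 weeks apart".

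Protocol 7.1 sends to irRC those "patients who progress with sum of target lesion is > 20 % then should use IrRC", which is a strict inequality. The SAP repeats only section 17.1 and does not define progression.

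**The concern.** Under a purely relative rule, the change that counts as progression shrinks with the sum. At the smallest sums the protocol admits, it may be no larger than the scatter between two readings of an unchanged lesion. The reference is also the lowest of several readings, so it tends to lie below the true size, and the gap widens as scans accumulate. A confirmatory scan compared with that same nadir inherits the error.

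A false irPD would bring forward the event in the secondary disease-free survival endpoint (1.2.1, 17.2), chiefly in patients with small residual disease. Section 12.0 takes patients off study at progression and refers to section 7 for its definition. Footnote D of section 6.0 then asks only for overall survival in those patients, so later scans might not correct the call. A late response could also be missed, although 7.4 itself says regressions may come later.

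**Working it through.** **The plan's own figure.** The documents state no figure for irPD. Their only computed result is the Simon design in 17.1 (stop at 4 or fewer of 18; reject at 11 or more of 33):

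P(reject | p) = Σ over x = 5 to 18 of P(Bin(18, p) = x) × P(Bin(15, p) ≥ 11 − x)

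This gives 0.0458 at p = 0.20 and 0.8011 at p = 0.40, so the stated 0.05 and 80% hold. They do not depend on the irPD rule.

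**Rise needed for irPD.** Required rise = 0.20 × nadir sum.

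| Nadir sum (mm) | 5 | 7 | 10 | 20 | 25 | 30 | 50 |
|---|---|---|---|---|---|---|---|
| Required rise (mm) | 1.0 | 1.4 | 2.0 | 4.0 | 5.0 | 6.0 | 10.0 |

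A change from 10 to 12 mm is exactly 20%. It meets the threshold in 7.4 but not the strict inequality in 7.1.

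**Chance of a false call in an unchanged lesion.** From the documents: threshold 20% over nadir, smallest target 10 mm, one un-ablated measurable site, scans about every 12 weeks. Assumed: normal reading error with SD 0.5 to 2 mm per sum, independent between scans, and readings rounded to whole mm. In the simulation the nadir is the running minimum including baseline. A false irPD is confirmed when a reading and an independent repeat are both at least 1.2 × that nadir. Four scans cover about 48 weeks.

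| Sum, rule | SD 0.5 | SD 1 | SD 1.5 | SD 2 |
|---|---|---|---|---|
| 10 mm, as written, four scans | 4% | 33% | 54% | 65% |
| 10 mm, as written, no rounding | 1% | 24% | 48% | 61% |
| 10 mm, as written, first scan only | 0.5% | 6% | 12% | 16% |
| 15 mm, as written, four scans | 0% | 8% | 27% | 43% |
| 20 mm, as written, four scans | 0% | 1% | 10% | 24% |
| 10 mm, plus 5 mm minimum, four scans | 0% | 0% | 2% | 11% |

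At 30 mm the four-scan figure is at most about 5%, reached at SD 2 mm, with or without a 5 mm minimum.

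**Sensitivity to the confirmation rule.** If the next scheduled scan serves as confirmation (three chances in four scans), a 10 mm sum gives 22, 38 and 47% at SD 1, 1.5 and 2 mm. If confirmation is only recommended and not done, a 10 mm sum at SD 1 mm gives 63% over four scans.

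**Where a 5 mm minimum would act.** 0.20 × nadir < 5 mm when nadir < 25 mm. Above that the 20% rule is already the stricter one.

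**The case against.** A reader might infer that a single 2 mm reading is scored as progression. The documents do not support that. Two of the three confirmation statements make irPD depend on a second scan, and 7.1 and 7.3 provide a repeat scan about a month after initial progression for patients who continue treatment. One such reading is unconfirmed irPD. What remains is that the confirmation statements disagree, and that a second comparison with the same low nadir reduces the error without removing it.

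The size rests on an assumed reading error. At SD 0.5 mm the problem nearly vanishes, and at sums of 15 mm or more it is then about 0% over four scans. So it cannot be said that an unchanged lesion is bound to cross the line. A single 10 mm target is also the entry floor. Up to five targets are allowed, and no distribution of baseline sums is given, so the share of the 33 patients exposed is unknown. These points stand and limit the claim to small sums.

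Protocol 7.1 names RECIST 1.1 as the first assessment, so any absolute minimum there may already apply at that step. If so, 7.4 restates the rule incompletely, because it writes out its own irPD definition without saying whether such a minimum carries over.

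Finally, irPR is measured from baseline, and 7.3 lets some patients continue treatment and scans after initial progression. A reader might infer that the primary result or the error rates of the Simon design are compromised. The documents do not show that.

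**Conclusion.** The gap is real and confined to small sums. Protocol 7.4 sets no minimum absolute increase, so 2 mm meets the irPD threshold at a 10 mm sum and 1 mm meets it at a 5 mm nadir. With an assumed SD of 1 to 2 mm, the chance of a confirmed false irPD in an unchanged 10 mm sum over four scans is about 33 to 65%. At 20 mm it is about 1 to 24%. At 30 mm the rule is largely unaffected.

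The effect falls mainly on the secondary progression-based endpoint. It could reach the primary response count only through patients who leave before a later response is seen or confirmed, and that route has not been quantified. The sample size, stopping rule, type I error and power in 17.1 are unchanged. This is a cheap improvement, not a flaw in the primary analysis.

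**What to change.** In 7.4, for endpoint scoring only, require both the 20% rise over nadir and a minimum absolute increase in the sum. Take the value from RECIST 1.1, which 7.1 and 7.4 name as the base; the 5 mm used here is an assumption.

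In the same edit:
- State one confirmation rule for irPD, with its interval and unit, in place of the three in 7.4.
- Reconcile the strict inequality in 7.1 with the at-least-20% threshold in 7.4.
- Reconcile the additional 10% rule for further progression in 7.3 with the same definition. On a 12 mm sum it amounts to 1.2 mm. What follows for treatment is for the sponsor to decide.

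The minimum itself costs one sentence. The downside is that true growth in sums below 25 mm would be called progression somewhat later.
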